7. STATISTICAL AND QUANTITATIVE ANALYSES

7.1 Statistical Methods

This is a phase II study of ixazomib in AML/MDS patients who have achieved CR/CRi after front-line or first salvage therapy. Up to 40 patients will be enrolled in the study with an estimated accrual rate of one patient per month. The additional follow up will be 12 months after the last patient enrolls in the study. The primary objective is to evaluate relapse-free survival (RFS). The study will monitor futility and toxicity.

7.1.1 Determination of Sample Size and Futility Monitoring

Futility will be monitored for the study. We will monitor RFS using the methods of Thall et al. (2005), and we will stop enrolling patients to the study if we have reason to believe that the median RFS is less than that from the historical data, which is around 11 months. The trial will be stopped if Pr(lamda(E) > lamda(S) | data from the trial) < 0.05, where lamda(S) is the median RFS for standard treatment in the historical data with an inverse gamma distribution IG(123, 1342), which corresponds to a mean of 11 months and a standard deviation of 1 month, the corresponding 95%CI of (9.2, 13.1) months. The prior for lamda(E) is assumed to be IG(3.21, 24.31), corresponding to a mean of 11 months and a larger standard deviation of 10. Futility monitoring will start once 10 patients have been enrolled. Assuming an accrual rate of 1 per month and an additional follow-up of 12 months, the operating characteristics for the futility stopping rule under various true states are summarized in the following table 1, with results based on 5000 simulations.

Median OS (M)	Prob(Stop Early)	Mean No. of Patients
		(25%, 75%)
17	0.012	39.6 (40, 40)
14	0.036	39.1 (40, 40)
11	0.164	36.8 (40, 40)
8	0.673	28.2 (17, 40)

Table 1: Operating characteristics for futility monitoring

5	1	14.2 (10, 17)

Multc Lean V2.1 and OneArmTTE Version 4.1.1 were used for the trial design. The Department of Biostatistics will provide and maintain a website ("Clinical Trial Conduct": https://biostatistics.mdanderson.org/ClinicalTrialConduct/) for futility monitoring for each treatment arm on this study. The Clinical Trial Conduct website resides on a secure server, and access is gained through usernames and passwords provided to personnel responsible for enrolling patients and updating patient data. The website is accessed through a browser using secure socket layer (SSL) technology. Personnel responsible for enrolling patients on trials, which includes the principal investigator(s), research nurse(s), and data coordinator(s), will be trained by members of the Department of Biostatistics in the use of the trial website; the importance of timely updating of follow-up times and recording of events will be emphasized in training.

7.1.2 Populations for Analysis

All analyses including the efficacy and safety analysis will include all patients who have received at least 1 dose of study drug.

7.1.3 Demographic and Baseline Characteristics

Demographic and baseline laboratory results will be summarized using descriptive statistics, including means with standard deviations, or medians with ranges, histograms and box-plot. Fisher's exact test and Wilcoxon rank test will be used in the data analyses of categorical and continuous variables, respectively. Survival or times to failure and time to progression functions will be estimated using the Kaplan-Meier method. The two-sided log-rank test will be used to assess the differences of time to events between groups, and Cox proportional hazards model will also be fitted to evaluate the association between tiem-to-event outcomes with patient characteristics.

7.1.4 Efficacy Analysis

It is expected that the median RFS time will be 11 months or higher under this study treatment. If the trial continues to maximum accrual of 40 patients and maintains sufficient follow-up to observe 25 events (relapse/death) with a median RFS of 11 months, then a 95% credible interval for median RFS would extend from 7.4 to 16.3 months. The median RFS time will be estimated by Bayesian posterior estimates, along with the 95% credible intervals.

7.1.5 Safety Analysis

Unacceptable toxicities will also be monitored closely using the method of Thall et al (1995). Denote the probability of unacceptable toxicity by T_E , where toxicity is defined as any clinically significant treatment-related grade 3 or higher toxicities. We assume $T_E \sim$ beta (0.3, 0.7). We will stop the study if at any time point $Pr(T_E > 0.30 | data) > 0.9$. That is, we will stop the trial if, at any time during the study, we determine that there is more than 90% chance that the unacceptable toxicity rate is more than 30%. The trial will be stopped if (the number of severe toxicity observed / among number of patients) \geq 4/5, 6/10, 8/15, 9/20, 11/25, 13/30, 15/35. The toxicity stopping rules were created for examining data in patient cohorts of size 5.The operating characteristics are listed in table 2.

Toxicity will be reported by type, frequency and severity. Highest toxicity grades per patient per course will be tabulated for selected adverse events and laboratory measurements.

True Prob(severe tox)	Pr(stop)	mean # Pts
0.1	0.0006	39.98
0.2	0.021	39.43
0.3	0.186	35.76
0.4	0.583	26.84
0.5	0.905	17.30

Table 2: OCs for unacceptable toxicity monitoring

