4. STUDY DESIGN

4.1 Overview of Study Design

This is an open-label single arm Phase II study in subjects with AML or high-risk MDS in CR/CRi. Patients will receive single 4mg oral dose of ixazomib on days 1, 8 and 15 of each 28-day cycle. Treatment with ixazomib will be administered for 12 cycles for patients who remain in CR.

For patients with MRD positive CR/CRi at study start, treatment with ixazomib may continue for a total of 12 cycles after achievement of MRD negativity is observed.

Patients who are experiencing clinical benefit may be eligible to continue therapy after the allotted 12 cycles after discussion with the PI and the discussion documented in the patient's medical record.

Subjects will be assessed for outcome status (i.e. maintenance of CR/CRi) every 3 cycles or as clinically indicated. Adverse events, compliance and concomitant medications will be assessed continually throughout the study; specific information will be requested at each study visit.

Study cycles will be administered every 28 days ± 5 days or upon resolution of any clinically significant study drug related AE to grade 0-1, whichever occurs first.

Administration of subsequent cycles should be administered when neutrophils recover to \geq

0.5 x 10⁹/L and platelets to \geq 50 x 10⁹/L, or to baseline levels prior to the start of the last cycle of therapy.

Ixazomib will be self-administered primarily on an outpatient basis; but may be administered as an inpatient. Patient compliance will be documented using the MD Anderson (MDACC) Research Medication Diary and will be assessed at each study visit.

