6.7 Management of Clinical Events

Adverse drug reactions such as thrombocytopenia, diarrhea, fatigue, nausea, vomiting, and rash have been associated with ixazomib treatment. Management guidelines regarding these events are outlined below. Further details of management of ixazomib AEs are described in Section 6 of the ixazomib IB.

Prophylaxis Against Risk of Reactivation of Herpes Infection

Patients may be at an increased risk of infection including reactivation of herpes zoster and herpes simplex viruses. Antiviral therapy such as acyclovir, valacyclovir, or other antivirals may be initiated as clinically indicated. Other antivirals are also acceptable.

Nausea and/or Vomiting

Standard anti-emetics including 5-hydroxytryptamine 3 serotonin receptor antagonists are recommended for emesis if it occurs once treatment is initiated; prophylactic anti-emetics may also be considered at the physician's discretion. Dexamethasone should not be administered as an anti-emetic. Fluid deficit should be corrected before initiation of study drug and during treatment.

Diarrhea

Prophylactic antidiarrheals will not be used in this protocol. However, diarrhea should be managed according to clinical practice, including the administration of antidiarrheals once infectious causes are excluded. Fluid intake should be maintained to avoid dehydration. Fluid deficit should be corrected before initiation of treatment and during treatment.

Erythematous Rash With or Without Pruritus

As with bortezomib, rash with or without pruritus has been reported with ixazomib, primarily at the higher doses tested and when given with agents where rash is an overlapping toxicity. The rash may range from limited erythematous areas, macular and/or small papular

bumps that may or may not be pruritic over a few areas of the body, to a more generalized eruption that is predominately on the trunk or extremities. Rash has been most commonly characterized as maculopapular or macular. To date, when it does occur, rash is most commonly reported within the first 3 cycles of therapy. The rash is often transient, self-limiting, and is typically Grade 1 to 2 in severity.

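### Table 2's toxicity stopping probabilities assume every patient's final toxicity status is known at each look, but Section 7.1.5 sets no assessment window, no rule for who counts at a look, and no single look schedule

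*Combined protocol and SAP*

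**What the plan says.** Section 7.1.5 of the combined protocol and SAP defines the monitored event without a time limit: "toxicity is defined as any clinically significant treatment-related grade 3 or higher toxicities". The prior is beta(0.3, 0.7), and the trial stops when there is a "more than 90% chance that the unacceptable toxicity rate is more than 30" percent. This is turned into boundaries of "4/5, 6/10, 8/15, 9/20, 11/25, 13/30, 15/35", applied to "the number of severe toxicity observed / among number of patients".

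On timing, the section says two things. The posterior criterion is worded so that it can be met at any moment in the study, but "The toxicity stopping rules were created for examining data in patient cohorts of size 5". Table 2 gives the probability of stopping and the mean number of patients for true toxicity rates from 0.1 to 0.5.

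Elsewhere:
- Section 4.1: "Treatment with ixazomib will be administered for 12 cycles for patients who remain in CR". Sections 4.1 and 4.3 allow longer treatment.
- Section 7.1: up to 40 patients, about one per month.
- Section 7.1.2: "All analyses including the efficacy and safety analysis will include all patients who have received at least 1 dose of study drug".
- Section 6.7, the only onset timing used here: "rash is most commonly reported within the first 3 cycles of therapy".

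No section defines a patient evaluable for the toxicity looks, requires minimum exposure before a patient counts, or holds accrual until a cohort has been assessed.

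**The concern.** A beta-binomial rule treats each patient as a completed trial with a known yes/no outcome. Here the outcome can occur at any time over roughly 11 months of treatment, while patients enter one month apart, so most patients at an early look are still at risk. If they are all in the denominator, toxicity still to come is counted as absent at that look. It enters the numerator at later looks, so the effect is a delay in reaching the boundary and, for some trials, a failure to reach it before accrual ends.

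At stake is how much protection the printed operating characteristics promise. This is the trial's only formal toxicity stopping rule, and Table 2 is what a review board would read to judge it. Table 1, for futility, is stated to assume an accrual rate and follow-up. Table 2 has no such statement.

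**Working it through.** **Inputs.** Prior, criterion, boundaries and cohort size: Section 7.1.5. Maximum of 40 patients and one per month: Section 7.1. Twelve 28-day cycles: Section 4.1. At 30.4375 days per month, 12 cycles are 336/30.4375 = 11.04 months and 3 cycles are 84/30.4375 = 2.76 months.

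**1. Boundaries.** With r toxicities in n patients the posterior is beta(0.3 + r, 0.7 + n - r). The smallest r with Pr(T_E > 0.30) > 0.9 is 4, 6, 8, 9, 11, 13, 15 at n = 5, 10, ..., 35, exactly as listed.

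**2. Table 2.** An exact binomial recursion over these looks, with every outcome known, starts at a 40% rate with 5(0.4)^4(0.6) + (0.4)^5 = 0.0768 + 0.0102 = 0.087 at n = 5 and accumulates over later looks. Results:

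| True rate | Pr(stop), recomputed | Pr(stop), Table 2 | Mean patients, both |
|---|---|---|---|
| 0.1 | 0.0006 | 0.0006 | 39.98 |
| 0.2 | 0.0214 | 0.021 | 39.43 |
| 0.3 | 0.1860 | 0.186 | 35.76 |
| 0.4 | 0.5827 | 0.583 | 26.84 |
| 0.5 | 0.9046 | 0.905 | 17.30 |

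The arithmetic is right. The condition behind it is complete outcomes at each look.

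**3. Exposure at the looks.** At a steady one per month and a look at the last entry, the first five patients have had 4, 3, 2, 1 and 0 months, averaging 2 months or 2/0.92 = 2.2 cycles. None of the first 10 has finished 12 cycles at n = 10, and 8 of 20 have at n = 20.

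**4. What the first look sees.** Take the look one month after the fifth entry, so exposures are 5, 4, 3, 2 and 1 months, at a 40% rate. The expected final count is 5 × 0.4 = 2. The expected count already observed is:
- onset uniform over cycles 1-3: 0.4 × (1 + 1 + 1 + 2/2.76 + 1/2.76) = 1.63;
- onset uniform over 12 cycles: 0.4 × (15/11.04) = 0.54.

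**5. Cohort looks, all dosed patients counted.** Simulation with the stated boundaries and looks at 5 to 35 (40,000 runs or more per setting). Onset patterns are assumed. Each cell gives true rates 40% / 50%.

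| Onset | Pr(stop), look one month after last entry | Mean patients, same look | Pr(stop), look at last entry |
|---|---|---|---|
| Table 2 | 0.583 / 0.905 | 26.84 / 17.30 | |
| All in cycle 1 | 0.58 / 0.90 | as Table 2 | 0.48 / 0.85 |
| Cycles 1-3 | 0.52 / 0.87 | 29.7 / 20.5 | 0.43 / 0.82 |
| Half in cycles 1-3, half in 4-12 | 0.35 / 0.75 | 34.4 / 26.9 | 0.28 / 0.67 |
| Uniform over 12 cycles | 0.26 / 0.65 | 36.1 / 29.8 | 0.20 / 0.57 |

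The first Pr(stop) column uses regular monthly entry. The other two columns use random (Poisson) entry at the same mean rate. Changing between the two moves Pr(stop) by about 0.02. Mean patients counts the cohort at the look and omits anyone who enters during the one-month wait.

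**6. Re-checking at every event.** Using the posterior boundary for the current number of patients (from n = 5, during accrual), Pr(stop) at 40% / 50% is about 0.65 / 0.93 for cycles 1-3, 0.48 / 0.85 for half and half (0.47 to 0.49 at 40%, depending on how entry times are generated), and 0.38 / 0.79 for uniform onset.

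**The case against.** A reader might infer that Table 2 simply overstates the protection, or that it holds only if all toxicity falls in the first month. The documents do not support either as a general statement, for three reasons.

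First, the denominator is not spelled out. Section 7.1.5 says only number of patients, and Section 7.1.2 defines analysis populations, not interim evaluability. Counting every dosed patient is the natural reading because nothing narrows it, but it is an inference. This point stands: the demonstrable gap is an unspecified denominator and window.

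Second, the criterion is also worded to apply at any time. If it is re-checked at every event, early-onset toxicity gives 0.65/0.93, above Table 2. This stands too, and it means the direction of the discrepancy depends on the reading. It does not rescue Table 2, which was computed for cohorts of 5 and falls above or below the event-driven rule according to onset.

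Third, the large shortfalls need late onset, which no passage documents. With the rash timing from Section 6.7 and a one-month lag, the loss is modest: 0.583 - 0.52 = 0.06 at 40% and 0.905 - 0.87 = 0.04 at 50%. Uniform onset is a pessimistic case. But the protocol gives no onset timing for treatment-related grade 3+ toxicity overall, so a range is the honest statement.

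Nor should it be inferred that recently entered patients are counted as toxicity-free for good: their later events enter the numerator at later looks.

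**Conclusion.** The concern holds in this form: Table 2 is arithmetically correct for a rule with immediately complete outcomes, and Section 7.1.5 does not specify such a rule. With cohort looks one month after the last entry and all dosed patients counted, the stopping probability at 40%/50% lies between about 0.52/0.87 and 0.26/0.65 for onset ranging from cycles 1-3 to uniform over 12 cycles. If all onset is in cycle 1, Table 2 is recovered with that lag. With event-driven checks the range is about 0.65/0.93 to 0.38/0.79. These figures rest on one patient per month, the stated boundaries, the inferred denominator and assumed onset patterns. They show that Table 2 cannot be relied on as printed, but they do not establish a particular loss of protection. This should be corrected. The prior and boundaries themselves are internally consistent.

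**What to change.** In Section 7.1.5:
1. Reconcile the wording that allows stopping at any time with the cohort-of-5 looks, and state one schedule, including how long after a cohort's last entry the look is taken.
2. State which patients are in the denominator at a look.
3. Restate Table 2, both Pr(stop) and mean number of patients, by simulation at one patient per month over a stated range of toxicity onset times. Keep all on-treatment grade 3+ toxicity in the monitored event.

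A tempting shortcut is to limit the event to the first 2 or 3 cycles and keep the boundaries. Table 2's Pr(stop) would then hold, but only for the within-window rate, and later toxicity could no longer stop the trial. For a 3-cycle window and whole-course rates of 40%/50%, Pr(stop) falls to about 0.02/0.07 with half-late onset and 0.001/0.002 with uniform onset. That change is not recommended.

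The cost is a few sentences and one rerun, with somewhat less favourable printed figures if toxicity is late.

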7.1.8. Study Endpoints

Relapse-Free Survival (RFS):

Is defined as the interval from the date of enrollment to the date of first objective documentation of disease relapse or death from any cause. Subjects who are lost to follow-up without documented relapse, or are alive at last follow-up without documented relapse will be censored at the date of their last response assessment.

Overall Survival (OS):

Time from date of treatment start until date of death due to any cause.

Complete Remission (CR):

Peripheral counts: No circulating blasts, neutrophil count $\ge 1 \ge 1 \ge 10^{9}$ /L and platelet count $\ge 100 \ge 10^{9}$ /L Bone marrow: $\le 5\%$ blasts, no detectable auer rods, no extramedullary leukemia with normal maturation of all cell lines. Persistent dysplasia will be noted.

Complete remission with incomplete count recovery (CRi):

Defined as a morphologic complete remission but the ANC may be $<1 \ge 10^9$ /L or the platelet count may be $<100 \ge 10^9$ /L.

Time to discontinuation from treatment will be assessed as an estimate of treatment failure/tolerability and is defined as the interval from the date of enrollment to the date of discontinuation. Subjects who are ongoing in treatment at the time of study closure will be censored at the date of last visit.

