4.3 Duration of Study

Treatment will continue until discontinuation due to relapse or disease progression, unacceptable toxicity, or completion of therapy. Completion of therapy includes 12 cycles of ixazomib. Note that in patients with MRD positive disease at study start, treatment may continue for 12 cycles after achievement of MRD negativity is observed. For patients experiencing clinical benefit, treatment may be continued beyond 12 cycles if in the best interest of the patient.

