6.3 Dose-Modification Guidelines

6.3.1 Recommended ixazomib Criteria for Beginning or Delaying a Subsequent Treatment Cycle & Dose Modifications for Treatment Associated Toxicity

Treatment with ixazomib will use a cycle length of 28 days. For a new cycle of treatment to begin, the patient must meet the following criteria:

- ANC must be ≥ 500/mm³ and platelet count must be ≥ 50,000/mm³, or have recovered to baseline hematologic values
- All other nonhematologic toxicity (except for alopecia) must have resolved to ≤ Grade 1 or to the patient's baseline condition

If the patient fails to meet the above-cited criteria for initiation of the next cycle of treatment, dosing should be delayed for 1 week. At the end of that time, the patient should be re-evaluated to determine whether the criteria have been met. If the patient continues to fail to meet the above-cited criteria, delay therapy and continue to re evaluate. The maximum delay before treatment should be discontinued will be 4 weeks or at the discretion of the Principal Investigator.

All decisions for dose adjustments will be made by the MD Anderson treating physician.

For dosing recommendations upon recovery, refer to Table 6-2 and Table 6-3. Dose adjustments different than those described below are acceptable after discussion with the PI, and will require documentation of the rationale for such action.

Table 6-1 MLN908 Dose Adjustments

Dose (mg)
4.0 mg
3.0 mg
2.3 mg
Discontinue

Dosage adjustments for hematologic toxicity are outlined in Table 6-2.

Criteria	Action	
Within-Cycle Dose Modifications		
 If platelet count ≤ 25 × 10⁹/L or ANC ≤ 0.50 × 10⁹/L on a ixazomib dosing day (other than Day 1) 	 ixazomib dose should be withheld. Complete blood count (CBC) with differential should be repeated twice weekly until the ANC and/or platelet counts have exceeded the prespecified values (see Section 6.3.1) on at least 2 occasions. Upon recovery, ixazomib may be reinitiated with 1 dose level reduction. 	
Dose Modifications for Subsequent Treatment Cycles		

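### Time to discontinuation has no rule for patients who finish the planned course; read literally, Section 7.1.8 counts them as events (a minor, cheap correction)

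*Combined protocol and SAP*

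**What the plan says.** Section 7.1.8 introduces the endpoint as follows: "Time to discontinuation from treatment will be assessed as an estimate of treatment failure/tolerability". It "is defined as the interval from the date of enrollment to the date of discontinuation", with no restriction by reason. The only censoring rule is this: "Subjects who are ongoing in treatment at the time of study closure will be censored at the date of last visit".

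Section 4.3 describes how treatment ends: "Treatment will continue until discontinuation due to relapse or disease progression, unacceptable toxicity, or completion of therapy". It adds: "Completion of therapy includes 12 cycles of ixazomib". Sections 4.1 and 4.3 allow longer treatment in two groups. Patients MRD positive at entry may receive 12 cycles after becoming MRD negative, and patients with clinical benefit may go on beyond 12 cycles.

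The timing comes from Section 6.3.1 ("Treatment with ixazomib will use a cycle length of 28 days"), Section 4.1 ("Study cycles will be administered every 28 days ± 5 days") and Section 7.1 ("The additional follow up will be 12 months after the last patient enrolls in the study"). Section 6.13 ties the end of study visit to stopping ixazomib and does not separate completers from other patients. Section 6.12 has the primary reason for withdrawal entered in the CRF.

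**The concern.** A measure of treatment failure or tolerability should separate patients who had to stop from patients who finished. This definition does not. A patient who takes all 12 cycles without relapse or toxicity and then stops as planned has a discontinuation date and is not on treatment at closure. Taken at face value, that patient has an event on the same footing as one who relapsed.

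At stake is how this one descriptive result reads. Section 7.1.3 plans Kaplan-Meier estimates for times to failure. If this endpoint is plotted that way, the curve will drop at about 11 months because the schedule ends there. If the rule is left open, someone will have to choose how to handle completers after the data are in.

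**Working it through.** The plan gives no expected median, rate or sample size for this endpoint, so there is no stated figure to reproduce. The check has four steps.

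**1. When planned completion falls.** 12 cycles × 28 days = 336 days; 336 / 30.4375 = 11.04 months. The last dose (cycle 12, day 15) is 11 × 28 + 14 = 322 days after the first, or 10.6 months. If all 11 later cycles shift by the full 5 days in one direction, completion falls at 336 ± 55 = 281 to 391 days, or 9.2 to 12.8 months. A single 4-week delay gives 364 days, or 12.0 months. Any gap between enrollment and first dose adds to these.

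**2. Whether the censoring rule catches completers.** The last patient enrolled has 12 months of follow-up. On schedule, that patient completes at 11.04 months, before closure. At one enrollment per month, the patient before has about 13 months, and so on back. Even the full window drift of 12.8 months would therefore leave only the last patient on treatment at closure. Longer delays could add a few late enrollees. For patients who stop at 12 cycles, the rule almost never applies.

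**3. Size at the planning median.** Assumptions, not document figures except the 11-month median (Sections 7.1.1 and 7.1.4): exponential relapse or death from enrollment, a constant monthly rate r of toxicity stops, and nobody continuing past cycle 12.

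Share still on treatment at completion = exp[−(ln 2/11 + r) × 11.04]. Median time to a stop for relapse, death or toxicity = ln 2 / (ln 2/11 + r).

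| r per month | On treatment at 11.04 months | Of 40 patients | Median (months) |
|---|---|---|---|
| 0 | 49.9% | 20.0 | 11.0 |
| 0.01 | 44.7% | 17.9 | 9.5 |
| 0.02 | 40.0% | 16.0 | 8.3 |
| 0.04 | 32.1% | 12.8 | 6.7 |

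In all four rows the median comes before 11.04 months, so relapse and toxicity set it, and censoring completers would not change it. The one sensitivity is the r = 0 row. If completion is dated to the last dose (10.58 months), exp[−(ln 2/11) × 10.58] = 51.3% are still on treatment, and the median would read 10.6 instead of 11.0.

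**4. When the median is affected.** The schedule fixes the median once more than half of patients reach completion. With true median RFS M and a fraction q stopping for other reasons by completion, the share reaching it is (1 − q) × 0.5^(11.04/M).

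- M = 17: 63.8%, 57.4%, 51.0% and 44.6% for q = 0, 10, 20 and 30%. The median reads 11.04 months for q up to 20%, where censoring completers would give not reached by the end of cycle 12. At q = 30% it is 9.5 months under either rule.
- M = 14: 57.9%, 52.1% and 46.3% for q = 0, 10 and 20%. The median is fixed for q up to 10%; at 20% it is 9.9 months under either rule.

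**The case against.** Several points on the other side stand.

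- **Section 4.3 has two readings.** Completion can be parsed as an alternative to discontinuation rather than a cause of it. Section 7.1.8 also speaks of an estimate of failure or tolerability and does not call every stop a failure. A reader might infer that the plan declares completers to be failures; it does not say so. But on the second reading a completer is neither an event nor censored, so the rule is still missing.
- **Planned duration does not dominate the curve at the planning median.** A reader might infer that the schedule, not tolerability, determines the result, or that the median cannot pass 11 months. Steps 3 and 4 do not support the first inference unless RFS is clearly longer than planned. Cycle windows, permitted delays and extended treatment undercut the second.
- **Continuation is allowed.** Patients still in remission after 12 cycles are plausible candidates to go on, so not everyone who reaches 336 days stops there.
- **No comparison by MRD status is specified.** One might infer that MRD-positive patients will look more tolerant because their planned course can be longer. That would follow only if someone ran the comparison, and MRD status is not in the subgroup list in Section 3.3.
- **The endpoint carries little weight.** It is absent from Sections 2 and 3 and drives neither sample size nor stopping. Tolerability is covered by adverse event incidence and severity (Section 3.2) and by the toxicity monitoring in Section 7.1.5.

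These points limit the consequence. None supplies a rule for completers.

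**Conclusion.** The gap is real and minor. Section 7.1.8 taken literally counts planned completion as an event; otherwise it leaves completers without a status. Nothing else in the document settles which.

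Under the assumptions in step 3, 32 to 50% of patients (about 13 to 20 of 40) would be miscounted. That is an upper bound under those assumptions, because Sections 4.1 and 4.3 allow continuation for MRD positivity at entry or clinical benefit. At an 11-month median RFS, the curve up to about 11 months and its median are essentially sound, and the artefact is the drop at and after planned completion. The schedule fixes the median only if RFS is clearly longer, for example a 17-month median with up to 20% stopping for other reasons. So the distortion is larger the better patients do. The primary analysis, the futility rule and the toxicity rule are untouched.

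**What to change.** Amend the definition in Section 7.1.8:

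- Define the event as stopping ixazomib for relapse or progression, toxicity, death, transplant, or withdrawal by patient or investigator.
- Do not count planned completion as a failure. Either censor at the date the patient actually stops as planned, or report cumulative incidence by reason for stopping with completion as its own category. The planned stop may come after 12 cycles, after the MRD-driven course, or after any clinical-benefit extension. Using the actual date keeps patients who are still on drug at risk, so a later stop for toxicity is not lost.
- Say which date marks completion, last dose or end of the last cycle, since the two differ by 14 days on schedule (336 − 322).

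Beyond 12 cycles the patients at risk are those selected to continue, so that part of any curve needs a caution whichever option is chosen.

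The cost is one paragraph. The primary reason for withdrawal is already in the CRF, and completion follows from the cycles given. Transplant has no entry of its own in the Section 6.12 list of reasons, so it should be identifiable within the category for other reasons. The small downside is reduced comparability with trials that count every stop. Treatment rules do not change.
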